4.3 Primary Objectives

4.3.1 SVR12

Purpose: To address the primary HCV virologic response objective to assess the proportion of participants who attain SVR12 in each study arm.

- a) Two-sided 90% confidence interval around the observed SVR proportion using the Wilson confidence limits, per protocol.
- b) Two-sided 95% confidence interval around the observed SVR proportion using Clopper-Pearson limits, to line up with the Gilead study (in consideration of joint manuscript).
- c) For the non-SVRs, reasons for failure will be provided: detectable HCV RNA after treatment discontinuation, HCV virologic failure (VF) as determined by the site, unavailable HCV RNA result, other.

Note on the primary HCV virologic endpoint:

1. SVR12 is defined in the protocol as HCV RNA < lower limit of quantification (LLOQ), either target detected (TD) or target not detected (TND), at 12 weeks after treatment discontinuation. The sample within the week R+12 visit window, as described in Section 2.6, which is closest to the targeted time will be used. If there is no HCV RNA sample within this window, then the participant will be considered SVR12 failure, unless there are preceding and subsequent HCV RNA measurements that are both <LLOQ (either TD or TND).
 2. Participants not providing SVR data (e.g. due to early study discontinuation) will be included and counted as SVR failures.
- ✓ SDAC Validation: Derivation of SVR12 variable will be validated. The analysis program that summarizes SVR12 and calculates confidence intervals will also be validated.
 - ✓ Data sources for the primary endpoint SVR12: HCVRNALDMS (LDMS data table), F1601 (off study CRF table), F4003 (off treatment CRF table), F0010 (patient visit CRF data table),

STATUS (data table on key patient characteristics and date variables including date of last dose of study treatment), CMW0029 (concomitant medication CRF table to censor data at initiation of alternate HCV treatment in case any participants erroneously remained on study when alternate HCV treatment was initiated), SPW0455 (HCV RNA specimen tracking CRF table).

4.3.2 Safety

Purpose: To address the primary safety objective.

- a) Number of participants meeting the criteria noted below. The worst graded event per person over time will be used.
- b) Summaries on all reported adverse events and laboratory events and listings described in Section 4.2.1 provide supplemental information on safety.

Notes on the primary safety endpoint:

1. Occurrence of Grade ≥ 3 or higher adverse event (diagnosis, sign, symptom or laboratory event), SAE according to ICH criteria, or AE reported as the reason for permanent discontinuation of study treatment during study treatment and up to 30 days after study treatment discontinuation.
 2. Event that is ongoing at the same grade from prior to study treatment initiation will be excluded.
-
- ✓ SDAC Validation: The program deriving the indicator variable on meeting the safety endpoint criteria as described above will be validated.
 - ✓ Data sources for the primary safety endpoint: EVW0314, EVW0315, F2860 (Hematology), F2861 (Chemistry), HXW0148 (Signs and Symptoms History), LBW0144 (Creatinine Clearance), STATUS (data table on key patient characteristics and date variables including date of last dose of study treatment), CMW0029 (concomitant medication CRF table to censor data at initiation of alternate HCV treatment in case any participants erroneously remained on study when alternate HCV treatment was initiated).

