No treatment-emergent deaths were reported in the LDV/SOF Phase III safety population and few participants (2.6%) had any SAE. The only SAEs reported in >1 participant across all treatment groups were noncardiac chest pain (three participants), and chest pain, colitis, gastroenteritis, hand fracture, hypertension, intervertebral disc protrusion, and pneumonia (two participants each), suggesting

that no trends in SAE type or onset time were observed. Only five participants (0.3%) had an SAE that was considered related to study drug by the investigator.

Grade 4 laboratory abnormalities were reported in only 1.0% of participants for both the RBV-free (LDV/SOF) and RBV-containing (LDV/SOF+RBV) groups. Grade 3 laboratory abnormalities were reported in 5.4% of participants in the RBV-free (LDV/SOF) groups and 11.4% of participants in the RBV-containing (LDV/SOF+RBV) groups. The increased incidence of Grade 3 laboratory abnormalities in the RBV-containing (LDV/SOF+RBV) groups compared with Grade 3 laboratory abnormalities in the RBV-free (LDV/SOF) groups was driven largely by hemoglobin abnormalities. The addition of RBV to a LDV/SOF treatment regimen contributed substantially to the incidence of anemia that required dose modification or discontinuation (hemoglobin <10 g/dL). A small number of participants with changes in non-hematologic laboratory parameters met the criteria for Grade 3 and 4 laboratory abnormalities. The most common Grade 3 or 4 chemistry laboratory abnormalities across all treatment groups were increased lipase (1.7%) and increased serum glucose (1.5%). In participants with Grade 3 or 4 increased lipase, no case of Grade 3 or 4 increased lipase was associated with clinical signs or symptoms of pancreatitis. Only one case of pancreatitis occurred in the entire Phase III program; this event occurred post treatment in a participant with a history of chronic pancreatitis and was not associated with a Grade 3 or 4 increased lipase. Among participants who experienced a Grade 3 or 4 increased serum glucose, all participants had a history of diabetes, were taking diabetes medication, or had glucose intolerance (denoted by HbA1c >6.0% at screening).

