NOTE: Inability to definitively determine genotype or a non-GT-1 will exclude the participant from study participation.

4.1.8 Prior virologic treatment failure with SOF-containing regimen (SOF/RBV, SOF/PEG/RBV, and SOF/SIM).

NOTE A: See section 6.3.3 for requirements for documentation of prior HCV treatment and response.

NOTE B: Prior virologic failure is defined as quantifiable HCV RNA at any time after receiving HCV therapy as prescribed that was not attributed to reinfection.

NOTE C: HCV reinfection is defined by (1) documentation of clearance of prior infection (as evidenced by prior positive anti-HCV Ab or HCV RNA) either spontaneously or after treatment with two negative HCV RNA a minimum of 3 months apart AND (2) positive HCV RNA after documentation of two negative HCV RNA obtained a minimum of 3 months apart *or* infection with a different HCV genotype from the prior infection.

4.1.9 Body mass index (BMI)  $\geq$  18 kg/m^2 within 42 days prior to study entry.

NOTE A: A BMI calculator is available at the DMC website (http://www.fstrf.org).

NOTE B: The height and weight measurement used to calculate BMI must be obtained on the same day.

- 4.1.10 The following laboratory values obtained within 42 days prior to study entry by any US laboratory that has a CLIA certification or its equivalent.
  - HCV RNA  $\geq 10^4$  IU/mL
  - Hemoglobin  $\geq$  12.0 g/dL for male,  $\geq$ 11.0 g/dL for female participants
  - Platelets  $\geq$  50,000/mm^3
  - International normalized ratio (INR) ≤1.5 x ULN unless participant has known hemophilia or is stable on an anticoagulant regimen affecting INR, in which case any INR value is acceptable
  - Albumin ≥ 3.0 g/dL
  - Creatinine clearance (CrCl) ≥ 60 mL/min, as calculated by the Cockcroft-Gault equation (refer to section 6.3.5 for calculator utility link)
  - Aspartate aminotransferase (AST) (SGOT) < 10 x ULN
  - Alanine aminotransferase (ALT) (SGOT) < 10 x ULN
  - Direct bilirubin  $\leq 1.5 \times \text{ULN}$
  - Hgb A1C ≤ 8.5%
- 4.1.11 Screening electrocardiogram (ECG) without clinically significant abnormalities as determined by the investigator within 42 days prior to study entry.
- 4.1.12 Willing and able to provide written informed consent.

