#### 6.3.7 Laboratory Evaluations

At screening and entry, all laboratory values must be recorded. For post-entry assessments, record all grades of creatinine and creatinine clearance and all other Grade  $\geq$ 3 laboratory values. All laboratory toxicities that led to a change in treatment (excluding indications for RBV dose reduction), regardless of grade, must be recorded.

All Grade 3 or higher laboratory values, any laboratory value that led to a change in treatment (excluding indications for RBV dose modification) or that met ICH, EAE, or SAE guidelines are defined by the protocol as reportable events that will require more detailed event reporting.

The study team should be notified ([contact]) of any new or worsened Grade  $\geq$  2 creatinine values, new or worsened Grade  $\geq$ 2 proteinuria or glucosuria after week 4 of study treatment.

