The study regimens have different treatment durations and, while the post-treatment follow-up time is the same for both study arms, the study durations are different in Arms A and B. Assessment of reasons for not achieving SVR12 is an important part of SVR12 and SVR24 analyses in this study, including loss to follow-up. Differential loss to follow-up in the two study arms may suggest the benefit of the shorter duration in the 12-week regimen or drawback of RBV intolerance. Either way, the SVR endpoints would capture the outcome of the regimen.

- 9.2 Outcome Measures
  - 9.2.1 Primary Outcome Measures
    - 9.2.1.1 SVR12 defined as HCV RNA < lower limit of quantification (LLOQ) (either target detected [TD] or target not detected [TND]) at 12 weeks after treatment discontinuation. The sample within the week R+12 (post-treatment) visit window, as defined in section 6.0, which is closest to the targeted time will be used. If there is no HCV RNA sample within this window, then the participant will be considered SVR12 failure, unless there are preceding and subsequent HCV RNA measurements that are both <LLOQ (either TD or TND).

    - 9.2.1.2 Occurrence of Grade 3 or higher AE (diagnosis, sign, symptom, or laboratory abnormality), SAE according to ICH criteria, or AE reported as the reason for permanent discontinuation of study treatment, during study treatment and up to 30 days after study treatment discontinuation. (Event that is ongoing at the same grade from prior to study treatment initiation will be excluded.)
  - 9.2.2 Secondary Outcome Measures
    - 9.2.2.1 Renal toxicity: (a) ≥ Grade 2 creatinine clearance after study entry, or
       (b) new proteinuria and/or glucosuria, defined as ≥ 1+ or an increase ≥ 1+ from baseline.
    - 9.2.2.2 SVR4 defined as HCV RNA < LLOQ (either TD or TND) at 4 weeks after treatment discontinuation. The measurement within the week R+4 visit window that is closest to the targeted time will be used. If there is no HCV RNA sample within this window, then the participant will be considered SVR4 failure, unless there are preceding and subsequent HCV RNA measurements that are <LLOQ (either TD or TND).

- 9.2.2.3 SVR24 defined as HCV RNA < LLOQ (either TD or TND) at 24 weeks after treatment discontinuation. Sample after 20 weeks after treatment discontinuation that is closest to the targeted time, not followed by any result ≥LLOQ, will be used.

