2.8 General Data Analysis Considerations

- Data summaries and analyses will be completed by study arm, unless specified otherwise. They will be collapsed across treatment arms for open interim reports.
- All participants who met the study eligibility criteria and received any study treatment will be included in the planned analyses, unless specified otherwise. The participants who are found to have been ineligible for the study after enrollment occurred will not be part of the planned analyses; if any of such participants received any study treatment, their safety profiles will be described separately in an appendix to the report.
- Participants are instructed to discontinue the study prior to initiation of non-study provided HCV treatment during follow-up after discontinuation of the study-provided treatment. If they remain on study in error, the data are censored at the time of alternative HCV treatment initiation.
- For the summaries on evaluations by study visits, calculated visit weeks will be used according to the tables shown above in Section 2.6. Entry value is defined as the evaluation from the day of treatment dispensation or the closest preceding evaluation. For the post-entry values, the evaluations conducted closest to the targeted dates will be used.
- For the summaries of AEs, diagnoses and opportunistic infections, events with the onset date on or after the study treatment initiation date will be summarized.
- In data lists, study participants will be identified by an anonymous patient identifier generated at the statistical center (publicID). Dates will not be shown, but converted to time (e.g. weeks) since randomization.
- Each Table/Figure/Listing will be annotated with the name and location of the program used to create it, including its location directory.
- Key outcome measures for which analysis programs require validation and the level of validation that is required are noted throughout the plan in Section 4.

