4.2.1 Adverse Events and Protocol-Required Laboratory Tests

- a) Descriptive tables summarizing the adverse events and the number of participants experiencing the events will be provided by grade and by the site report on relationship to study treatment.
- b) Summary table of all diagnoses reported.
- c) Listing of participants with renal toxicity events (defined as Grade ≥ 2 creatinine clearance post-entry or new proteinuria or glucosuria, an increase from entry glucosuria or proteinuria by $\geq 1+$).
 - baseline characteristics: age, sex, race/ethnicity, ART regimen, study treatment, cirrhosis status
 - all available results on: urinalysis protein and protein, creatinine clearance (CrCl), spot protein and creatinine (and protein/creatinine ratio)
 - study treatment modifications
 - study treatment adherence
 - ARV modifications

Notes:

1. The protocol requires grading of events according to The Division of AIDS Table for Grading the Severity of Adult and Pediatric Adverse Events, Version 2.0, November 2014, which is available on the RCC website: <http://rsc.tech-res.com/safetyandpharmacovigilance/gradingtables.aspx>
2. The protocol requires the collection of signs and symptoms, diagnoses, laboratory events that
 - a. are Grade ≥ 3 post-entry
 - b. that led to a change in treatment (excluding indications for RBV dose modification) regardless of grade, or
 - c. that met ICH, EAE or SAE guidelines regardless of grade.

In addition, all creatinine, creatinine clearance (CrCl) and urinalysis results are required. Urine spot protein and creatinine are repeated in participants who develop new proteinuria or glucosuria, an increase from entry glucosuria or proteinuria by $\geq 1+$, or who develop an increase in creatinine of 0.4 from entry or CrCl < 50 , until resolution.

3. Summary tables are based on events reported on the following forms: EVW0314, EVW0315, F2860 (Hematology), F2861 (Chemistry), LBW0144 (Creatinine Clearance) and will not explicitly include events reported on EAEs to DAIDS. Before the database is finalized, the data manager will ensure that all EAE events deemed 'reportable' and included in the SDMC AR001AES table are reflected on the study CRFs.
 4. Events with date of onset or specimen date prior to the first study treatment dose will be excluded.
 5. Deaths will be described separately and not included in the safety summary tables.

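### The primary safety exclusion covers only an unchanged grade, so a laboratory abnormality improving from Grade 4 at entry to Grade 3 on treatment is counted while a persistent Grade 4 is not

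*SAP*

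**What the plan says.** Protocol 9.2.1.2 defines the primary safety outcome as "Occurrence of Grade 3 or higher AE (diagnosis, sign, symptom, or laboratory abnormality), SAE according to ICH criteria", or an adverse event given as the reason for permanently stopping study treatment, from treatment start to 30 days after its end. SAP 4.3.2 repeats this and adds the counting unit: "The worst graded event per person over time will be used". Both texts carry the same baseline exclusion: "Event that is ongoing at the same grade from prior to study treatment initiation will be excluded". Neither says how to classify an event that continues at a lower grade, and neither says what *ongoing* means for a series of laboratory results.

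Two date rules sit elsewhere in the SAP. Section 2.8, for summaries of adverse events, diagnoses and opportunistic infections, says "events with the onset date on or after the study treatment initiation date will be summarized". Section 4.2.1 Note 4, under the supporting adverse event and laboratory tables, says "Events with date of onset or specimen date prior to the first study treatment dose will be excluded". SAP 4.3.2 refers to neither as a filter on the primary outcome.

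On data capture, Protocol 6.3.7 says "At screening and entry, all laboratory values must be recorded". After entry, all grades are recorded for creatinine and creatinine clearance. Other laboratory values are recorded only at Grade 3 or higher, or when they led to a treatment change.

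**The concern.** A baseline exclusion should remove abnormalities that the regimen did not worsen. This one is tied to equality of grade. A participant who enters at Grade 4 and stays there is left out. A participant who enters at Grade 4 and improves to Grade 3 is still at Grade 3 or higher, is no longer at the entry grade, and so meets the endpoint. Improvement is scored as a safety event and no change is not.

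This is one of two primary outcomes. SAP 4.3.2 also requires the program that derives the indicator to be validated against the criteria as written. Validation would therefore confirm this behaviour rather than catch it.

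**Working it through.** The documents give no expected rate, threshold or power for the safety outcome, so there is no planned figure to reproduce. Three checks were made.

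**1. Do the date rules close the gap?**
- SAP 2.8 names adverse events, diagnoses and opportunistic infections, not laboratory values. If it applies to 4.3.2, it removes a sign, symptom or diagnosis that began before treatment, whatever its later grade.
- SAP 4.2.1 Note 4 removes specimens taken before the first dose. A Grade 3 specimen taken on treatment passes.
- Neither rule is cited in 4.3.2, so their reach to the primary outcome is inferred.

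The gap is therefore essentially a laboratory one.

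**2. Classification of laboratory courses.** Entry grade comes first, then on-treatment grades. Reading A excludes any value equal to the entry grade. Reading B excludes values only while the entry grade is unbroken. Reading B′ is B applied to what the case report form normally holds, which is Grade 3 or higher only.

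| Course | A | B | B′ | Count only if Grade ≥3 and above entry grade |
|---|---|---|---|---|
| 4→3 | counted | counted | counted | not counted |
| 3→3 | not counted | not counted | not counted | not counted |
| 3→2→3 | not counted | counted | not counted | not counted |
| 4→3→4 | counted | counted | counted | not counted |
| 3→4 | counted | counted | counted | counted |
| 2→3 | counted | counted | counted | counted |
| 0→3 | counted | counted | counted | counted |

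An unchanged Grade 4 behaves like the 3→3 row. The 4→3 and 4→3→4 courses are counted under every reading of the present text. The 3→2→3 course depends on the undefined word. The last column drops only courses never worse than entry and keeps every worsening.

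**3. Size of one reclassified participant.** Protocol 9.6 specifies 95% Wilson intervals for safety. With p = x/n and normal quantile z, the limits are

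[p + z²/(2n) ± z√(p(1−p)/n + z²/(4n²))] / (1 + z²/n).

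As a check on the formula, 18/20 at 90% (z = 1.645) has centre (0.900 + 0.0676)/1.1353 = 0.852 and half-width 1.645 × 0.0787/1.1353 = 0.114. That gives 73.8% to 96.6%, as in Protocol Table 9-1; all seven rows of that table are reproduced.

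At 95%, moving one participant from counted to not counted:

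| Denominator | 1 counted | 0 counted | Shift (1/n) |
|---|---|---|---|
| 20 (planned arm) | 5.0% (0.9 to 23.6) | 0% (0 to 16.1) | 5 points |
| 7 (all enrolled) | 14.3% (2.6 to 51.3) | 0% (0 to 35.4) | 14.3 points |
| 4 (assumed arm) | 25.0% (4.6 to 69.9) | 0% (0 to 49.0) | 25 points |
| 3 (assumed arm) | 33.3% (6.1 to 79.2) | 0% (0 to 56.1) | 33.3 points |

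The split of the 7 participants by arm is not given; 3 and 4 is an assumption.

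**The case against.** The strongest answer is that the exclusion does not stand alone. Onset dating in SAP 2.8 already disposes of clinical events that began before treatment, and the remaining case is narrow. Version 2.0 covers 7 participants in a descriptive report made up mainly of listings, no test or stopping decision rests on the count, and an affected case could be described individually. Over-counting is also the cautious direction for safety. Most of this stands and limits the weight of the point. It does not make the rule right, since no safety purpose is served by counting an improved value and omitting an unchanged one.

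A reader might infer more than the documents support:

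- *That every abnormality which dips and returns to its entry grade is counted.* This holds only if *ongoing* means unbroken. Outside creatinine and creatinine clearance, the intermediate Grade 2 value would normally not be recorded, so the course would appear as 3 then 3 and be excluded.
- *That the entry criteria show how often this happens.* HbA1c is allowed up to 8.5% but is measured only at screening, so it cannot produce an on-treatment event. For INR, participants with hemophilia or on a stable anticoagulant are admitted with no limit ("in which case any INR value is acceptable"), but INR and lipids are scheduled on treatment only at weeks 12 and 24. Total bilirubin and lipase have no entry limit and are measured at every visit. However, the grading table is not reproduced, so the documents do not show which entry values would reach Grade 4.
- *That the phase III background shows the problem occurring.* Protocol 2.3.15 says of the Grade 3 or 4 glucose cases that "all participants had a history of diabetes, were taking diabetes medication, or had glucose intolerance". It gives no entry grades. All of these could have been genuine worsening, which any sensible rule counts.
- *That the phase III Grade 3 laboratory rates, 5.4% without and 11.4% with ribavirin, measure the false counts.* They do not separate worsening from persistence, and the protocol attributes the excess largely to hemoglobin, which has an entry minimum.

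**Conclusion.** The point stands for laboratory abnormalities. As written, a Grade 4 entry value that improves to Grade 3 meets the primary safety endpoint and an unchanged Grade 4 does not, and neither date rule repairs this. A second, smaller gap is that *ongoing* is undefined for repeated laboratory values and often could not be verified from the recorded data.

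For clinical events the exclusion is adequate provided SAP 2.8 governs 4.3.2, which should be said rather than assumed. Frequency cannot be estimated. The 1/n shifts describe one hypothetical participant, not an expected error. With 7 participants and a descriptive report this is a low-weight correction, but it corrects a stated rule for a primary outcome and costs almost nothing.

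**What to change.** In Protocol 9.2.1.2 and SAP 4.3.2 Note 2:

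1. Exclude a pre-existing event when it is at the same **or a lower** grade than at entry.
2. For laboratory values, count a Grade 3 or higher result only if its grade is above the entry grade, taken from the last value on or before the first dose. This removes the need to interpret *ongoing* for laboratory series.
3. List separately any on-treatment Grade 3 or higher laboratory values at or below the entry grade.
4. State that the onset dating in SAP 2.8 applies to the clinical-event limb.

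The serious-event and discontinuation limbs do not change. The comparator should be the entry grade rather than the highest screening grade. Screening can be up to 42 days before entry, and an abnormality that resolved by entry and then recurred on treatment should still count.

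The cost is a few sentences and one comparison in a program that is already to be validated, using entry values already recorded. The small downside is that a recurrence at the entry grade appears in the listing rather than in the count.
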